## Exploratory outcomes

Clinical characteristics of participants with non-traumatic hospitalizations and deaths in PLHIV with presumptive TB (to be reported in a separate manuscript).

TB prevalence: Prevalence of active TB diagnosed at enrolment, defined as TB diagnosed clinically or microbiologically through the TB investigations completed up to a maximum of 28 days after enrolment.

## Safety endpoints

Definitions of SAEs, and AESIs are provided below.

The study team will gather as much information as possible about all possible SAEs and AESIs. Information will be gathered about TB diagnoses, timing of ART initiation

(relative to TB diagnosis and treatment), clinical course (including documentation of relevant diagnostic and therapeutic activities by routine clinical staff), and alternative explanations for clinical symptoms. This information is a narrative clinical report compiled by the study physician using all available information from facility records, staff, patient and relatives and including judgment of study physician, National PI or delegate. Events possibly linked to TB-IRIS were presented to an independent expert clinical committee for adjudication about likelihood that symptoms are consistent with TB-IRIS. The adjudication committee will be blinded to arm allocation.

### Surveillance for SAEs and AESIs

SAEs are solicited in three ways:

- Active inquiry at 26 (22-30) week study visit
- Register reviews and referral to study team by routine staff in case of relevant medical complaints
- Tracing with phone calls and home visits between week 31 and 40 to determine outcome for participants without a documented clinic visit between week 22 and 30

AESIs are captured through referral to study team by routine staff in case of relevant medical complaints. We will not inquire about AESIs at the 26 (22-30) weeks study visit or during the tracing because the long recall period will not allow for adequate documentation of AEs other than SAEs.

### Definition of AEs

Adverse event (AE)	Any untoward medical occurrence in a trial participant, including occurrences that are not necessarily caused by or related to that trial procedures.
Adverse event of special interest (AESI)	AE consistent with TB IRIS (see section 7.1.3 for definition) according to judgment of independent clinical expert committee
Serious adverse event (SAE)	Any AE that: 
 
○ Results in death
 
○ Is life-threatening
 
○ Requires hospitalization or prolongation of existing hospitalization 
 
○ Hospitalizations due to uncomplicated delivery are not considered as SAE
 
 
 
○ Results in persistent or significant disability or incapacity
 
○ Consists of a congenital anomaly or birth defect
 

Definitions of causality for SAEs are as follows

Unrelated	There is no evidence of any causal relationship
Unlikely related	There is little evidence to suggest that there is a causal relationship (for example, the event did not occur within a reasonable time after administration of the trial procedures). There is another reasonable explanation for the event (for example, the patient's clinical condition or other concomitant treatment).
Possibly related	There is some evidence to suggest a causal relationship (for example, because the event occurs within a reasonable time after administration of the trial procedures). However, the influence of other factors may have contributed to the event (for example, the patient's clinical condition).

Probably related	There is evidence to suggest a causal relationship and the influence of other factors is unlikely.
Definitely related	There is clear evidence to suggest a causal relationship and other possible contributing factors can be ruled out.

### Definition of TB-IRIS

We will use the Meintjes et. al. [9] definition of paradoxical and unmasking TB-IRIS.

Paradoxical TB IRIS	
(A) Antecedent requirements	
Both of the two following requirements must be met:	
	
 
Diagnosis of tuberculosis: the tuberculosis diagnosis was made before starting ART and this should fulfill WHO criteria for diagnosis of smear-positive pulmonary tuberculosis, smear-negative pulmonary tuberculosis, or extra-pulmonary tuberculosis
 
Initial response to tuberculosis treatment: the patient's condition should have stabilised or improved on appropriate tuberculosis treatment before ART initiation—e.g., cessation of night sweats, fevers, cough, and weight loss. (Note: this does not apply to patients starting ART within 2 weeks of starting tuberculosis treatment since insufficient time may have elapsed for a clinical response to be reported)
 

(B) Clinical criteria	
The onset of tuberculosis-associated IRIS manifestations should be within 3 months of ART initiation, re-initiation, or regimen change because of treatment failure. Of the following, at least one major criterion or two minor clinical criteria are required:	
Major criteria	
 
New or enlarging lymph nodes, cold abscesses, or other focal tissue involvement—e.g., tuberculous arthritis
 
New or worsening radiological features of tuberculosis (found by chest radiography, abdominal ultrasonography, CT, or MRI)
 
New or worsening CNS tuberculosis (meningitis or focal neurological deficit—e.g., caused by tuberculoma)
 
New or worsening serositis (pleural effusion, ascites, or pericardial effusion)
 

Minor criteria	
 
New or worsening constitutional symptoms such as fever, night sweats, or weight loss
 
New or worsening respiratory symptoms such as cough, dyspnea, or stridor
 
New or worsening abdominal pain accompanied by peritonitis, hepatomegaly, splenomegaly, or abdominal adenopathy
 

(C) Alternative explanations for clinical deterioration must be excluded if possible	
	
 
Failure of tuberculosis treatment because of tuberculosis drug resistance
 
Poor adherence to tuberculosis treatment
 
Another opportunistic infection or neoplasm (it is particularly important to exclude an alternative diagnosis in patients with smear-negative pulmonary tuberculosis and extrapulmonary tuberculosis where the initial tuberculosis diagnosis has not been microbiologically confirmed)
 
Drug toxicity or reaction
 

Unmasking tuberculosis-associated IRIS	
Patient is not receiving treatment for tuberculosis when ART is initiated and then presents with active tuberculosis within 3 months of starting ART	
AND one of the following criteria must be met:	
	
 
Heightened intensity of clinical manifestations, particularly if there is evidence of a marked inflammatory component to the presentation. Examples include tuberculosis lymphadenitis or tuberculosis abscesses with prominent acute inflammatory features, presentation with pulmonary tuberculosis that is complicated by respiratory failure due to adult respiratory distress syndrome, and those who present with a marked systemic inflammatory syndrome related to tuberculosis.
 
Once established on tuberculosis treatment, a clinical course that is complicated by a paradoxical reaction
 

## 6.2 Analysis methods

Outcomes will be summarized using means and standard errors for continuous variables and numbers and percentages for categorical variables, by randomized arm.

### Primary outcome analysis

The primary analysis for this study will be the comparison of viral suppression rates between the two study arms. For the primary outcome, we will summarize the numbers and percentages of participants included in the analysis, and experiencing the intercurrent events, as per Tables 2a and 2b.

The analysis will use a modified Poisson regression with a log link and robust standard errors to calculate risk differences (10,11). The model will be adjusted for country, the pre-specified randomization stratification factor. (12) Moreover, we will adjust for the most important baseline characteristics (age, gender, CD4 cell count, and ART status) if found to be unbalanced between study arms. In the case of convergence issues, we will use marginal standardization to obtain the risk differences (13).

For the non-inferiority comparison between the two arms, a CI approach will be used. A figure illustrating the confidence intervals for the risk differences and the non-inferiority margin will be presented. If the lower bound of the confidence interval for the risk difference does not include the non-inferiority margin, then the intervention will be considered non-inferior.

For the non-inferiority comparison in the per-protocol analysis, we will use weighting techniques to re-weight the population (14) to account for a potential lack of exchangeability introduced by excluding individuals where the offer of ART did not follow the intervention strategy.

In addition to the absolute effect measure of risk differences, we will report the relative effect of the intervention as well with odds ratios and risk ratios as recommended by the CONSORTs statement (6).

As per section 3.4, if the intervention is found to be non-inferior to the control arm in both the ITT and per-protocol population, then we will assess for superiority under the superiority comparison approach (Table 2a) by assessing whether the 95% CI for the risk difference excludes 0.

We will conduct a complete case analysis in which only individuals with a valid VL measurement in the endpoint window of 22 to 30 weeks is included.

We will summarize what proportion of the primary outcome information came from tracing activities.

We will conduct a planned subgroup analysis by country. Effect estimates of the primary outcome will be presented descriptively by subgroup. Potential effect modification of the primary outcome by ART status will be assessed by including interaction term between arm and the corresponding variable in the model. If the interaction term is found to be

significant ( $p<0.1$ ), effect estimates will be summarized descriptively by subgroup. The study is not powered for these pre-planned subgroup analyses so all results will be considered exploratory.

Given that VLs were done through the routine health system, in Malawi, some DBS tests were done on platforms with a limit of quantification at 839 copies/mL (Abbott m2000/real time) or 883 copies/mL (Panther Hologic). After conferring with experts, we have concluded to consider these tests as suppressed at the limit of 400 copies/mL for the primary analysis if the PCR target was not detected (as opposed to target detection but not quantifiable). As a sensitivity analysis of the primary outcome, we will consider these as not suppressed.

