Study Intervention:	
“ART first” arm:
 
 
- ART initiation on the day of enrolment independent of TB investigations
 
 
“TB results first” arm:
 
 
- ART initiation only after active TB has been refuted or confirmed
 

Number of Participants with Rationale:	
Based on the assumptions of non-inferiority of the primary outcome between the two arms, proportions of viral suppression at 26 weeks of 75% in both arms and selection of a non-inferiority margin of 10%, a power of 80%, and a one-sided alpha level of 0.025, a sample size of 590 participants will be required.

Study Duration:	First participant in: October 2022. Expected recruitment period to reach sample size: 18 months. Follow-up duration: maximum 40 weeks. Last participant out: December 2024.
Study Centre(s):	Seven primary or secondary health care facilities in Lesotho and four primary health care facilities in Blantyre district, Malawi.
Statistical Considerations:	We will perform a non-inferiority comparison between the arms on the primary outcome of viral suppression at 26 weeks. Under the assumptions of the sample size calculation, the proportion of viral suppression in the “TB results first” arm is expected to be 75% and the non-inferiority margin is set at 10%. For analysis, we will use a confidence interval approach. We will do the comparison using both a per-protocol (PP) and a modified intent-to-treat (mITT) population. If the lower bound of the 95% confidence interval for the risk difference excludes -10% in both the PP and mITT population, then the intervention will be considered non-inferior. If the “ART first” arm is found to be non-inferior to the “TB results first” arm, then we will assess for superiority using the mITT set.
GCP Statement:	This study will be conducted in compliance with the protocol, the current version of the Declaration of Helsinki, the ICH-GCP as well as all national legal and regulatory requirements.

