#### 9.2.1 Primary analysis

The primary analysis for this study will be the comparison of viral suppression rates between the two study arms. Individuals who do not have documented VL 22 – 40 weeks after enrolment, died, transferred out without a documented VL, or were lost to follow-up will be considered to have a negative outcome (i.e., not achieved viral suppression). The analysis will use a logistic regression model adjusted for the pre-specified randomization stratification factors. Moreover, we will adjust for the most important baseline characteristics if found to be unbalanced (gender, age, ART naive vs reinitiating ART, number and type of TB symptoms) between study arms. For the non-inferiority comparison between the two arms, a CI approach will be used. A figure illustrating the confidence intervals for the risk differences and the non-inferiority margin will be presented. If the lower bound of the confidence interval for the risk difference does not include the non-inferiority margin, then the intervention will be considered non-inferior. Primary analyses for the non-inferiority comparison will be performed on the mITT, per-protocol, and complete case sets. If the “ART first” arm is found to be non-inferior to the “TB results first” arm in the mITT and per-protocol sets, then we will assess for superiority using the mITT set. Further details will be provided in the statistical analysis plan.

As a sensitivity analysis for the primary analysis, primary endpoint information obtained from the tracing visit will not be included.

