### 3.3 Sample size

As per the protocol: The sample size has been calculated with regard to the primary endpoint of the study. Secondary endpoints were not considered for the determination of the sample size. The expected proportion with viral suppression at 26 weeks after enrolment in the “TB results first” arm is 75%.

To test the hypothesis of non-inferiority of the primary outcome between the two arms, we set the non-inferiority margin to 10%, the power to 80%, and a one-sided alpha level of 0.025. These assumptions yield a sample size of 295 participants per arm.

If participants were found to be ineligible post-randomization and before recruitment ended (primarily for TB investigations happening prior to enrolment), they were replaced in order to reach the required sample size of 295 eligible participants per arm. Additional participants found to be ineligible after randomization will be excluded without replacement. Female participants becoming pregnant after enrolment will not be excluded.

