### 3.7 Timing of outcome assessments

Baseline is defined as the date of randomization. Time will be measured from randomization.

Baseline laboratory results are defined as those measured at the time of screening to a maximum of 14 days after screening. Of note, the time of a laboratory result is defined as the time when the sample was taken, not the time when the sample was processed or result available. Any laboratory tests done to establish a TB diagnosis and completed within 28 days of enrolment are considered for the establishment of prevalent TB.

Table 2 shows the nominal activity weeks and the permitted ranges as defined in the protocol, and as defined for analysis. The analysis windows are chosen to be as inclusive (wide) as possible while retaining clinical relevance, and without overlap between the windows for different activities. For the primary outcome and secondary outcomes of viral load, if there is more than one measurement recorded within the allowed time window, then any evidence of viral suppression within the window will be considered. For all other measurements and outcomes, if there is more than one measurement within a given interval, then the value will be taken that is within the protocol defined window but closest to the nominal activity day.

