### 5.5 Baseline patient characteristics

Baseline characteristics will be summarized by randomized group, using medians and interquartile ranges for continuous variables and numbers and percentages for categorical variables. A shell table showing the variables and categories is included in section 8. Assessment will be made for baseline imbalances between the randomization arms by visual inspection by the trial steering committee before looking at outcome data. The primary analysis will be adjusted to include any covariates so identified (erring on the side of inclusivity). There will be no formal testing of baseline characteristics across randomized groups (5,6).

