### **6.3 Missing data**

Missing baseline and outcome data will be summarized by study arm. Where applicable, percentages will be of non-missing values.

In the case of missing VL for the primary endpoint, when no information is available, the participant is considered to have failed (see Table 2a and 2b). However, in the case where a VL result was not available, but information about ART refills is available, we will consider using multiple imputation in a sensitivity analysis if the numbers of these cases is sufficient to warrant the additional complexity.

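### The primary model adds covariates beyond country only if they look unbalanced, under two SAP rules that conflict; one list should be fixed and used whatever the balance

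*SAP*

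**What the plan says.** Four places bear on which covariates enter the primary model.

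- **SAP 6.2, Primary outcome analysis.** Country, the stratification factor, is always in the model. In addition the analysts will "adjust for the most important baseline characteristics (age, gender, CD4 cell count, and ART status) if found to be unbalanced between study arms". The section does not define imbalance.
- **SAP 5.5, Baseline patient characteristics.** "Assessment will be made for baseline imbalances between the randomization arms by visual inspection by the trial steering committee before looking at outcome data". It continues: "The primary analysis will be adjusted to include any covariates so identified (erring on the side of inclusivity". The table to be inspected is the shell table in SAP 8.2. No numerical threshold is given, and the clause is not confined to the four variables in 6.2.
- **Protocol 9.2.1.** Adjustment is for the stratification factor and for the main baseline characteristics "if found to be unbalanced (gender, age, ART naive vs reinitiating ART, number and type of TB symptoms) between study arms". CD4 is absent. The section leaves further details to the SAP.
- **SAP 6.3 and 3.7.** On missing covariates the SAP says only: "Missing baseline and outcome data will be summarized by study arm". On timing: "Baseline laboratory results are defined as those measured at the time of screening to a maximum of 14 days after screening".

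The risk difference is to come from a modified Poisson model with a log link. Marginal standardization is named only as a fallback if the model fails to converge.

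**The concern.** The two SAP rules give different models from the same data. If fever or WHO stage looks unbalanced, 5.5 brings it into the primary model and 6.2 does not. If age looks balanced, neither rule includes it, however well it predicts suppression. Functional forms are not stated, nor whether a participant with a missing covariate is dropped.

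Beneath this lies a question of method. Under randomization an observed imbalance is due to chance. What makes a covariate worth adjusting for is its relation to the outcome, which is known or judged beforehand and does not depend on the observed balance. A balance trigger therefore leaves out useful covariates in some realizations and lets in useless ones in others.

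At stake are the reproducibility of the model behind the non-inferiority decision (required in both the ITT and per-protocol analyses) and the superiority step that follows, and a small amount of precision.

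CD4 raises a further point. Laboratory values up to 14 days after screening count as baseline, while the ART-first arm is offered ART on the day of enrolment. A CD4 count used for adjustment could thus be sampled after treatment has begun in one arm.

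**Working it through.** **1. The plan's own figure.** Inputs: "proportions of viral suppression at 26 weeks of 75% in both arms and selection of a non-inferiority margin of 10" percentage points (Protocol synopsis), and "we set the non-inferiority margin to 10%, the power to 80%, and a one-sided alpha level of 0.025" (SAP 3.3), with 295 per arm.

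- SE of the risk difference = √(2 × 0.75 × 0.25 / 295) = 0.03565.
- Half-width of the 95% CI = 1.96 × 0.03565 = 6.99 points.
- Power = Φ(0.10 / 0.03565 − 1.96) = Φ(0.845) = 80.1%.

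The stated 295 per arm reproduces with no covariates at all, so the sample size does not depend on this point.

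**2. How often chance would trip the trigger.** The SE of a standardized mean difference (SMD) is √(2/295) = 0.082. The documents give no threshold, so three are shown as stand-ins for the eye. SAP 8.2 has 27 variables by my count, 26 besides country, each treated here as one scalar.

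| Trigger on abs(SMD) | One variable flagged | At least one of the four in SAP 6.2 | Expected number of 26 |
|---|---|---|---|
| 0.05 | 0.544 | 96% | 14.1 |
| 0.1 | 0.225 | 64% | 5.8 |
| 0.2 | 0.015 | 6% | 0.4 |

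Column 3 is 1 − (1 − p)⁴, which assumes independence; column 4 is 26p. The primary model could contain almost nothing beyond country or more than a dozen extra variables, depending on an unstated visual standard.

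**3. What always adjusting is worth.** As an approximation, adjustment multiplies the variance by (1 − R²), where R² is the share of outcome variance explained beyond country. The documents give no R²; 4 to 10% is assumed.

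- R² = 4%: SE = 0.03565 × √0.96 = 0.03493, half-width 6.85 points, power 81.7%.
- R² = 10%: SE = 0.03565 × √0.90 = 0.03382, half-width 6.63 points, power 84.0%.

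**4. Compared with a trigger.** Simulation with 40,000 trials per setting, 295 per arm, 75% in both arms, the four SAP 6.2 covariates, country always in the model, and a linear model with robust SE as a stand-in for the SAP's model. Power in %:

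| R² | Never | Trigger 0.2 | Trigger 0.1 | Trigger 0.05 | Always |
|---|---|---|---|---|---|
| 4.1% | 80.0 | 80.1 | 80.4 | 80.8 | 81.4 |
| 5.8% | 80.2 | 80.3 | 80.9 | 81.5 | 82.2 |
| 9.7% | 79.9 | 80.1 | 81.2 | 82.3 | 83.6 |

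The gain from always adjusting is 0.5, 0.7 and 1.2 points over the 0.05 trigger, 0.9, 1.3 and 2.3 over the 0.1 trigger, and 1.3, 1.9 and 3.5 over the 0.2 trigger. Differences were taken before rounding; their Monte Carlo SE is 0.05 to 0.13 points.

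**5. Type I error.** At a true difference of −10 points (20,000 trials, R² 5.8% and 9.7%), the one-sided error was 0.020 to 0.024 with a trigger and 0.023 to 0.025 with a fixed list. Neither exceeds 0.025.

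**6. The model proposed below.** Modified Poisson with marginal standardization, CD4 in four categories plus 10% not available, 10,000 trials per setting. Power for country only against the fixed list was 80.7 v 81.8, 80.1 v 82.1 and 79.6 v 83.2 at the same three R² settings. Type I error was 0.027 for the fixed list and 0.023 for country only (Monte Carlo SE 0.002), both compatible with 0.025.

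**The case against.** **The protocol's list is not a serious conflict.** Protocol 9.2.1 defers to the SAP, and the SAP also replaces the protocol's logistic model without saying so. This stands: the decisive conflict is inside the SAP, between 5.5 and 6.2. One sentence on the protocol list is still worth having.

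**SAP 5.5 is a procedure and not a third list.** Also true, so the documents hold two named lists and one open rule.

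**The effect is small and rests on assumptions.** True. The trigger closest to the SAP's stated leaning towards inclusion is the loose one, where the gain is 0.5 to 1.2 points. The 3.5-point figure needs both the strictest trigger and the largest R². The 14.1 expected flags need an eye that reacts to an SMD of 0.05, and that count uses the 26-variable reading while the power figures use the four-variable reading.

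**A stronger reading is tempting and should be resisted.** A reader might infer that the open rule lets the model be chosen to favour non-inferiority. In a separate simulation of 4,000 trials per setting, picking the most favourable of the 16 subsets of the four covariates gave false non-inferiority in 3.1 to 4.6% of trials (R² 2 to 10%). That choice requires outcome data, and SAP 5.5 places the decision before outcomes are looked at. A mechanical balance rule in the same simulation kept the error at about 2.5%. The documents do not support a claim of inflated error or lost planned power.

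**Late CD4 samples have not been shown to do harm.** Correct. CD4 is scheduled at enrolment (Protocol 6.3 and 6.12), and the documents give no count of later samples. The timing rule below is a precaution.

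**It may be too late.** SAP version 2.0 is dated 14 January 2025, after the planned last participant out in December 2024. The documents do not show whether outcomes have since been seen by arm, so the fix must allow for both cases.

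**Conclusion.** The point holds as a matter of pre-specification first and precision second. SAP 5.5 and 6.2 cannot both govern the primary model, and neither defines imbalance. Replacing the trigger with a fixed list removes the ambiguity and, if the four covariates explain 4 to 10% of outcome variance, gains about 0.5 to 1.2 power points over a loose trigger and up to 3.5 over a strict one. Both the R² range and the thresholds are assumptions. Type I error, the 295 per arm and the planned 80% power are unaffected. The change should be made because it costs no participants and no new data; the trial's validity does not hang on it.

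**What to change.** Before outcomes are seen by arm, amend the SAP as follows.

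- **6.2:** name one covariate set, used whatever the observed balance, for both the ITT (the protocol's mITT) and per-protocol analyses. An example is country plus the four variables 6.2 already names: age, sex, ART status and baseline CD4. The final choice is the investigators', on prognostic grounds. In the per-protocol analysis, fit the same outcome model with the planned weights.
- **Forms and missing values:** state, for example, age as linear and CD4 in fixed categories with an extra category for not available, so that nobody is dropped for a missing covariate.
- **5.5:** delete the visual-inspection trigger and the open-ended clause. The baseline table stays as description.
- **Protocol list:** state that the new list supersedes the one in Protocol 9.2.1, including its TB-symptom covariates.
- **Risk difference:** make marginal standardization the default. List this as a change, since 6.2 now has it only for convergence problems.
- **CD4 timing:** for adjustment, use only samples taken on or before the day of randomization, by the same rule in both arms; code later samples as not available.
- **Sensitivity:** keep the country-only model as a sensitivity analysis.

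If outcomes have already been seen by arm, report the fixed-list model as a post hoc sensitivity analysis instead.

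The cost is SAP wording. The variables are already collected. Some CD4 values may become not available; the documents do not allow a count.
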